## 1.6 Phase I Trial of EGFR AS in Patients with Recurrent SCCHN

Previous studies have reported negligible toxicity following intratumoral administration of DNA. Our preclinical studies suggest that 60 µg of antisense DNA decreases tumor progression. Therefore, we implemented a rapid dose escalation (100% increment increase between tiers) in the phase I clinical study of EGFR AS. Eligible patients had recurrent SCCHN and have previously failed other treatments. Patients received weekly intratumoral injections for 4 weeks. The dose of EGFR AS was escalated in successive cohorts of patients (classic “3+3” design) as follows: level 1 - 60 µg/60 µL, level 2 - 120 µg/120 µL, level 3 - 240 µg/240 µL, level 4 - 480 µg/480 µL, level 5 - 960 µg/960 µL, and level 6 - 1.92 mg/1.92 mL. A total of 17 patients were enrolled. We reported results at the ASCO 2007 meeting. No grade 3 or 4 or any dose limiting toxicities were observed at any dose level. A dose of up to 1.92 mg/1.92 mL of EGFR AS was well tolerated. There were four adverse events related to EGFR AS in this trial. All events were grade 1 and included two episodes of injection site pain/swelling, one episode of edema and one episode of lethargy. No dose limiting toxicities were observed at any dose level. One patient developed dehydration that was thought to be unrelated to the drug injection. Five of 17 patients (29%) achieved an objective response: 2 patients had a complete response and 3 patients had a partial response. In order to demonstrate transfection of the EGFR AS gene into the tumors, we performed polymerase chain reaction (PCR) analysis on DNA extracted from pre- and post-treatment patient tissue specimens. We were able to detect EGFR AS in the tissue specimens taken two weeks after the last EGFR AS injection in both non-responders and responders. Moreover, we observed that STAT3 and EGFR expression levels at baseline correlated with efficacy outcomes. The final manuscript is in preparation.

## 1.7 Study Rationale

The incorporation of novel targeted therapies to radiation therapy is of particular interest in head and neck cancer, and may improve efficacy without significantly increasing toxicity. Cetuximab is an EGFR inhibitor that is a potent radiosensitizer and has increased the survival of patients with stage III/IV head and neck cancer when added to radiation therapy. We would like to enhance the standard therapy of locally advanced SCCHN by incorporating intratumoral EGFR AS injections, a novel and promising locoregional treatment, to standard radiation and cetuximab. We hypothesize that the addition of a second EGFR-targeted agent that inhibits EGFR at the intracellular level will improve the antitumor effect of standard radiation and cetuximab. Preliminary preclinical data from our group support this hypothesis. Based on our data, intratumoral EGFR AS therapy has shown promise as single treatment modality. The addition of EGFR AS to standard radiation and cetuximab may further increase treatment efficacy and is of major interest. The goal of this study is to evaluate the safety, efficacy, and secondarily, the biologic effects in patients with locally advanced SCCHN of an antisense gene targeting the EGFR in combination with standard therapy

with radiation and cetuximab, a systemic EGFR inhibitor.

## 2. OBJECTIVES

- To evaluate the safety of the combination of intratumoral EGFR AS DNA with standard cetuximab and radiation.
- To evaluate the locoregional control (primary endpoint), in patients with locally advanced SCCHN treated with intratumoral EGFR antisense DNA combined with standard radiation plus cetuximab.
- To evaluate the toxicities associated with the above treatment.
- To evaluate other efficacy parameters, including the objective response rate, distant control and overall progression-free survival, and overall survival.
- To determine the effect of EGFR antisense therapy on EGFR and EGFR-related biomarkers. We will use reverse phase protein microarrays (RPPA) and immunohistochemical (IHC) analysis of tissue microarrays (TMA), on baseline and post-treatment tumor tissue, to determine the expression level and modulation of a panel of EGFR and EGFR-pathway related biomarkers, including (but not necessarily limited to) EGFR, pEGFR, Src, pMAPK, STAT3, pSTAT3, pSTAT5, pSTAT1, pAKT, p38, p21, p27, PARP, E-cadherin, p-ErbB3, and Ki67. We hypothesize that the baseline expression or modulation of one or more EGFR signaling proteins will correlate with objective response rate and locoregional control after combined modality treatment.
- To examine the transfection of the EGFR antisense gene therapy in vivo.

## 3. SELECTION OF PATIENTS

### 3.1 Eligibility Criteria

- First stage  
Patients with AJCC 7th edition stage IVA-IVC or recurrent or metastatic head and neck cancer will be eligible. Patients with M1 disease must have asymptomatic or low volume distant metastasis and require palliation for local and regional disease.
- Second stage (phase II part)  
Patients with AJCC 7th edition stage III-IVB (T1-4, N1-3M0) head and neck cancer, except WHO type II and III nasopharyngeal cancer, including unknown primary tumors.
- Histologically or cytologically confirmed diagnosis of squamous cell carcinoma or variants or poorly differentiated carcinoma.
- Unidimensionally measurable disease (RECIST criteria).
- ECOG Performance Status of 0-2
- In the second stage of the study, therapy will be administered with a curative intent and patients should not have recurrent disease or distant metastasis.
- Primary tumor and/or lymphadenopathy should be technically suitable for intratumoral injections. The Otolaryngologist specialist on the head and neck team will determine this feasibility.

- Participating patients should agree to undergo a tumor biopsy at baseline as well as approximately 2 weeks later as specified in study schema.
- Prior treatment
  - First stage: any prior treatment, except prior therapy, which specifically and directly targets the EGFR pathway, administered within the last 6 months. No prior radiation therapy to the head and neck.
  - Second stage: no prior chemotherapy, biologic/molecular targeted therapy (including any prior therapy which specifically and directly targets the EGFR pathway), or radiotherapy for head and neck cancer.
- Prior surgical therapy will consist only of incisional or excisional biopsy, including tonsillectomy, and organ sparing procedures, including neck dissection. Any non-biopsy surgical procedure for head and neck cancer must have taken place at least one month before initiating protocol treatment, at the treating physician's discretion.
- Patients must have organ and marrow function as defined below:
 

Absolute neutrophil count	1,000/ $\mu$ L
Platelets	75,000/ $\mu$ L
Hemoglobin	$\geq$ 10 g/dL
Total bilirubin	<2 x upper normal institutional limits
Creatinine clearance	> 20 mL/min
- Age of 18 years.
- Because radiation therapy is known to be teratogenic and EGFR inhibitors may have teratogenic potential, women of childbearing potential and men must agree to use adequate contraception (hormonal or barrier method of birth control) prior to study entry and for the duration of study participation, and for 3 months after completing study treatment. Should a woman become pregnant or suspect she is pregnant while participating in this study, she should inform her treating physician immediately.
- Informed consent must be obtained from all patients prior to beginning therapy. Patients should have the ability to understand and the willingness to sign a written informed consent document.

### 3.2 Exclusion Criteria

- Severe renal insufficiency (creatinine clearance < 20 mL/min)
- Treatment with anticoagulants, except when used to maintain the patency of a central venous line, or INR >1.5, or PTT ratio >1.5.
- Uncontrolled intercurrent illness including, but not limited to, ongoing or active infection or psychiatric illness/social situations that would limit compliance with study requirements. Significant history of uncontrolled cardiac disease; i.e., uncontrolled hypertension, unstable angina, uncontrolled congestive heart failure.
- Patients may not be receiving any other investigational agents.
- No history of prior malignancy, with the exception of curatively treated squamous cell or basal carcinoma of the skin or in situ cervical cancer, DCIS or LCIS of the breast, localized early stage

prostate cancer, or malignancy that has been treated with a curative intent with a 3-year disease-free survival.

- Pregnant women are excluded from this study because cetuximab, EGFR AS, and radiation have the potential for teratogenic or abortifacient effects. Because there is an unknown but potential risk for adverse events in nursing infants secondary to treatment of the mother with cetuximab and EGFR AS, breastfeeding should be discontinued if the mother is treated with cetuximab. The effects of cetuximab and EGFR AS on the developing human fetus at the recommended therapeutic dose are unknown. For this reason women of child-bearing potential and men must agree to use adequate contraception (hormonal or barrier method of birth control) prior to study entry and for the duration of study participation. Should a woman become pregnant or suspect she is pregnant while in this study, she should inform her treating physician immediately.
- HIV-positive patients receiving combination anti-retroviral therapy are excluded from the study because of possible drug interactions with cetuximab. Appropriate studies will be undertaken in patients receiving combination anti-retroviral therapy when indicated. HIV status of the patient will be obtained from the patient's history via discussion with the investigator. HIV testing is not required.
- Prior severe infusion reaction to a monoclonal antibody.
- Patients who are not informed of and are not willing to comply with the investigational nature of the study and have not signed a written informed consent in accordance with institutional and good clinical practice guidelines.
- Phase 2 **ONLY** (second stage) – Subjects with M1 disease will be excluded.

## 5. TREATMENT PLAN

- Loading dose of cetuximab 400 mg/m^2 IV over 120 minutes 2 weeks prior to starting radiation.
- Cetuximab 250 mg/m^2 IV over 60 minutes weekly, the week prior and during days of radiation, until radiation is completed (diphenhydramine hydrochloride [Benadryl] premedication 30-60 minutes prior to cetuximab infusion as required, see 5.1).
- Intratumoral EGFR AS injections weekly x 7 weeks (or less if there is no identifiable tumor), starting 2 weeks prior to radiation and after cetuximab is administered. Subsequent EGFR AS injections can be given before or after cetuximab is administered. Injections will be in the primary and/or lymph nodes. One site will be injected per weekly session. The intratumoral EGFR AS injections should occur during the same calendar day due to CTRC scheduling. If it is necessary the antisense injection can be scheduled within 1 business day of the original schedule date and then resume the original schedule.
- EGFR AS will be administered by direct intratumoral injection using direct visualization, endoscopy, or imaging-guidance (ultrasound) as clinically determined. The same lesion (primary tumor or lymph node) will be injected during treatment.
- Radiation therapy 70 Gy, 200 cGy/daily, 5 days/week (see 5.3). Radiation will start on a Monday, Tuesday, or Wednesday. Cetuximab will be given prior to radiation.
- A tumor biopsy will be performed prior to starting cetuximab and 2 weeks later but prior to starting radiation.
- In the first stage, after three (3) subjects are enrolled and have received all EGFR AS injections, there will be a two-week waiting period to assess adverse events before enrolling additional subjects. After the two-week period, additional subjects may be enrolled.

### 5.1 Cetuximab Administration

In an effort to prevent an infusion reaction, all patients should be premedicated with diphenhydramine hydrochloride [Benadryl] 50 mg (or an equivalent antihistamine) by IV given 30-60 minutes prior to the first dose of cetuximab. Premedication may be administered prior to subsequent doses, but at the Investigator's discretion, the dose of diphenhydramine (or a similar agent) may be reduced.

The initial dose of cetuximab is 400 mg/m^2 intravenously administered over 120 minutes, followed by weekly infusions at 250 mg/m^2 IV over 60 minutes. The infusion rate of cetuximab must never exceed 5 mL/min. Patients must be continuously observed during the infusion for signs of anaphylaxis.

Patients will be closely monitored for treatment-related adverse events, especially infusion reactions (see management of cetuximab adverse events) during the infusion and the post-infusion observation hour, if necessary. For the initial cetuximab infusion, vital signs should be monitored pre-infusion, ½ hour into the infusion, and at the end of the infusion, and, if needed, 1 hour post-infusion. For subsequent infusions, vital signs should be taken pre- and post-infusion; however, it is recommended that the patient be observed for 1 hour post infusion. Patients who have developed an infusion reaction in the past will be observed for >1 hour, if necessary.

For the duration that patients are on study therapy, adverse event monitoring will be done continuously. Patients will be evaluated for adverse events at each visit and are to be instructed to call their physician to report any adverse events between visits.

## 5.2 Intratumoral EGFR AS

### Injections

The treatment will be administered in the outpatient setting. Pretreatment tumor biopsies will be performed in the operating room at the time of diagnosis or in the outpatient setting under local anesthesia. Intralesional (primary tumor or cervical metastases) EGFR AS will be administered weekly until there is no identifiable tumor or a maximum of 7 weeks.

- EGFR AS will be administered by direct intratumoral injection using direct visualization, endoscopy, or imaging-guidance (ultrasound) as clinically determined. Injection sites may be treated before injection with EMLA cream (or equivalent) to minimize discomfort. The primary tumor or cervical metastases will be injected with a single dose of DNA and monitored. The tumor will be inoculated with a 25-gauge needle in an attempt to maximize the distribution of the gene transfer formulation in the injected lesion. Specifically, the needle will be introduced into the center of the tumor and the injection will be performed slowly as the needle is withdrawn from the tumor. Each dose will be given 7 days (+/- 2 days) after the previous dose. The same lesion (primary tumor or lymph node), which will be the dominant and most accessible, will be injected during treatment in each patient. In the first stage, after three (3) subjects are enrolled and have received all EGFR AS injections, there will be a two-week waiting period to assess adverse events. After the two-week period, additional subjects may be enrolled.

To determine the *in vivo* efficacy of the antisense gene and the consequences of EGFR antisense gene therapy, we will obtain tumor biopsies under local anesthesia in the

outpatient setting, at the time or after the second dose of EGFR AS and after the second cetuximab dose, in addition to the pretreatment biopsy. Therefore, the tumor will be biopsied 2 times. When possible, we will biopsy adjacent areas of the tumor at each time point to determine heterogeneity of transfection and EGFR expression. When possible, additional biopsies will be obtained from non-injected areas that are more than 2 cm apart from an injection site. A comparison of biopsies from injected and non-injected lesions will provide the opportunity to assess the added effect of EGFR AS. Prior injection sites will be marked and attempts will be made to perform biopsies in the area of prior inoculation(s). Biopsies will be delivered to [name]'s laboratory at CTRC and to [name] laboratory at UPCI for molecular studies. The presence of EGFR antisense DNA in the tumors will be determined using PCR. EGFR and EGFR pathway will be evaluated using RPPAs and IHC (see correlative studies section).

[name] or  
[name].  
Co-Director, Preclinical Research  
CTRC Institute for Drug Development  
Assistant Professor  
Department of Medicine/Division of Hematology and Medical Oncology  
University of Texas Health Science Center at San Antonio  
[name]  
[name]  
[name]  
[contact]  
Email: [contact]  
Email: [contact]

[name]  
University of Pittsburgh  
Head and Neck Cancer Signaling Laboratory  
[name]  
[name]  
[contact]  
Email: [contact]

#### EGFR AS Dose

Patients will receive a total EGFR AS dose of 1.92mg/1.78mL on each weekly treatment. This dose may be delivered equally in the same tumor site per weekly session, the primary tumor or cervical lymph nodes.

#### Dose/Schedule Modifications

There will be no dose reductions. However, weekly doses will be omitted in the setting of locoregional toxicities (even if those are thought to be related to radiation).

Based on prior experience, the expected toxicities of EGFR AS therapy may include local discomfort at the injection site, edema, bleeding and cutaneous erythema when the treatment is administered.

Treatment with EGFR AS will be held in the setting of grade 3 or 4 mucositis/dermatitis.

Treatment with EGFR AS will be discontinued if there is cellulitis at the injection site requiring antibiotic therapy or grade 4 locoregional toxicities within the injected site develop (such as bleeding or tissue necrosis).

#### Duration of Therapy

Each patient will receive up to 7 weekly treatments. Treatment may be discontinued earlier if there is no identifiable tumor, a patient withdraws from study, develops intolerable toxicities, or their disease progresses (see section 7.8).

#### Gene Transfer Efficiency and Biologic Activity

These studies require a tissue biopsy and will be performed prior to initiation of therapy and on the second week of therapy. Tumor tissue will be biopsied for molecular studies as defined elsewhere. In order to demonstrate transfection of the EGFR AS gene into the tumors, we will perform polymerase chain reaction (PCR) analysis on DNA extracted from pre- and post-treatment patient tissue specimens. Samples will be taken directly to [name] laboratory and the assays will be performed under her direction at the time points indicated above. Samples from San Antonio will be sent to [name] via [name]'s laboratory.

### 5.3 Radiation therapy

Radiation therapy will be standard of care for participating institutions.

#### 5.3.1 Physical Factors

Equipment: Linear accelerator with appropriate photon and electron energies for supplemental boosting to the nodes.

Photon energies of 4 to 6 MV and/or appropriate electron energies for boosting the nodes are allowed. Photon energies > 6 MV may be utilized when appropriate to boost target localized centrally.

Minimum treatment distance must be  $\geq 80$  cm SSD (or SAD for isocentric techniques).

#### 5.3.2 Localization Requirements

##### 5.3.2.1 Simulation

Simulation of all fields is mandatory. Patients must be reproducibly

immobilized. Radio-opaque markers should be used to delineate the extent of nodal disease and whenever possible, the primary tumor, if conventional treatment planning is used. The use of customized Cerrobend blocks or multileaf collimator is recommended to shape the field and limit dose to normal structures. For CT simulation, IV contrast is recommended and the data should be acquired using 3 mm slice width and spacing using the spiral mode of scanner.

#### 5.3.2.2 Verification

Checking the films should be done weekly. Beam portal films must be obtained to each field.

5.3.2.3 Electron fields utilized for supplemental nodal boosting must be verified by portal verification, simulation, or diagram.

### 5.3.3 Radiation Dose

Treatment to the primary tumor and upper neck will be given at 2 Gy/fraction once each day, five days a week. A total dose of 70 Gy/35 fractions/7 weeks will be delivered. Fields must be reduced to exclude the spinal cord at 36 Gy with dose calculated in the central plane. The entire neck must be irradiated to a total dose of at least 46- 50 Gy (even in N0 stage) at anatomic levels of lymph nodes usually 2-4 cm beneath the skin surface. Clinically positive neck nodes should also receive a dose of 70 Gy/35 fractions given continuously for 7-8 weeks. An electron beam should be used to supplement the dose to the posterior cervical chain nodes after the spinal cord has been shielded. Hence, the total dose to the primary tumor and clinically positive nodes will be 70 Gy. The anterior lower neck will be treated at 2 Gy/fraction once a day (3 cm depth or at depth determined by 3D imaging) from the anterior to a total dose of 46-50 Gy/25 continuous fractions (if clinically negative) in 5 weeks. The maximum dose permitted to the spinal cord will not exceed 45 Gy as determined by a separate off-axis point dose calculation.

### 5.3.4 Target Volume Irradiation and Radiation Doses

5.3.4.1 A combination of lateral opposing fields are recommended for the treatment of the primary tumor site and upper neck. A single anterior AP field will be used to treat the lower neck below the fields of the primary tumor/upper neck. When there is clinically involved lymph nodes in the lower neck, an additional posterior (PA) field may be necessary to deliver a supplemental dose to the positive nodes. All fields must be treated at each treatment session. The upper and lower fields should be matched using a "three dimensional" technique (i.e., appropriate rotation of the treatment table and appropriate angulation of the collimator or beam split technique). However, if such a three-dimensional match is not possible, the upper neck and supraclavicular fields may be abutted at the skin. The latter case, a small block should be placed either in the lower lateral position in the upper neck fields, or in the midline of the anterior

supraclavicular field (whichever is appropriate and does not block tumor) to the shield areas of potential overlap of diverging beams over the spinal cord.

#### 5.3.4.2 Upper Neck Primary Volume

The primary treatment fields should encompass the primary tumor and/or suspected lymph node disease in the upper neck using the shrinking field technique as follows:

The initial target volume should include the primary tumor, positive nodes with an approximately 3.0 cm margin and the next echelon of uninvolved lymphatic nodal drainage sites to a dose of 50 Gy. Included in the target volume is the first field reduction occurring off the spinal cord at 36 Gy.

The second field reduction will occur at 50 Gy and continue to 60 Gy with the new target volume encompassing the primary tumor and known areas of nodal disease as well as areas at high risk for lymph node involvement with approximately 2.0 cm margin.

The third and final field reduction will occur at 60 Gy and continue to 70 Gy with the new target volume encompassing the primary tumor and known areas of nodal disease with at approximately 1.0 cm margin.

As a general rule, both ipsilateral and contralateral posterior cervical nodal chain and the adjacent echelon of uninvolved lymphatic nodal drainage sites will be treated to a dose of 46-50 Gy/5 weeks.

#### 5.3.5 Lower Neck Volume

A single lower neck field will be used to treat the lower neck and the supraclavicular fossae. When there is (are) positive node(s) in the lower neck, an additional posterior field may be necessary to deliver a supplemental dose to the positive node(s). The boost dose should not exceed 4 Gy.

The lower border of the lower neck field will be just below the clavicular head with appropriate margins when there are positive nodes in the supraclavicular fossa. The lateral borders of the lower neck field will extend to the intersection of the sternocleidomastoid muscle and the clavicle.

For all patients with clinically positive nodes greater than 6 cm, or with clinically positive supraclavicular nodes, a mediastinal "T" field may be used. The lateral limbs of the T field will extend below the clavicular heads with margin, and the central portion of the field extends 5 cm more inferiorly to include the upper mediastinum.

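### For conventional fields, the dose provisions for clinically positive lower-neck nodes do not agree: 70 Gy total, a 4 Gy boost limit, a 70 Gy maximum, and no stated base dose

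*Combined protocol and SAP*

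**What the plan says.** All references are to the combined protocol and SAP.

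- **5.3.3 Radiation Dose** sets the nodal dose with no distinction between upper and lower neck: "Clinically positive neck nodes should also receive a dose of 70 Gy/35 fractions given continuously for 7-8 weeks". It then concludes: "Hence, the total dose to the primary tumor and clinically positive nodes will be 70 Gy". The anterior lower-neck field is treated at 2 Gy per fraction "from the anterior to a total dose of 46-50 Gy/25 continuous fractions (if clinically negative) in 5 weeks". The same section sets 46-50 Gy as a minimum for the whole neck.
- **5.3.4.1** describes a single anterior field for the lower neck. Where nodes there are involved, "an additional posterior (PA) field may be necessary to deliver a supplemental dose to the positive nodes". No amount is given.
- **5.3.5 Lower Neck Volume** repeats that arrangement and follows it at once with a number: "an additional posterior field may be necessary to deliver a supplemental dose to the positive node(s). The boost dose should not exceed 4 Gy".
- **5.3.6 Boost Doses** allows further boosts to persistent tumor or positive nodes, or to make up for long interruptions. It too sets a limit of 4 Gy, and explains it as a 70 Gy maximum.
- **5.3.11.2** (IMRT) gives involved nodes 70 Gy at 2 Gy per fraction, with no 4 Gy limit. The **Low Neck** text that follows allows either IMRT or an anterior field matched to the IMRT fields, and refers back to the doses already set out.

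**The concern.** A team using conventional fields for a patient with a positive lower-neck node meets two instructions. One gives a total of 70 Gy. The other is written for this very case; it describes a supplement on top of the lower-neck field and limits the boost to 4 Gy. Whether the two agree depends on the dose to which the 4 Gy is added, and that dose is missing. The upper neck is handled differently: 5.3.4.2 sets out its field reductions at 50 Gy and 60 Gy and a final 70 Gy.

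The first thing at stake is the dose a patient receives. The second is the phase II result. The primary endpoint in 11.1 is 1-year locoregional PFS, tested in 31 evaluable patients in a single arm against a null of 68% built from a historical rate. Eligibility for that stage is written as N1-3, and 5.3.5 expressly expects positive lower-neck and supraclavicular nodes. If teams read the text differently, nodal dose will vary for reasons unrelated to EGFR AS. With no concurrent control, any effect on regional control could not be separated from that of the study agent. Section 11.1 also plans to compare progression in injected and non-injected regions, and uneven nodal dose could confound that comparison.

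**Working it through.** **Inputs**

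- Total for positive nodes: 70 Gy in 35 fractions of 2 Gy (5.3.3).
- Lower-neck field dose, clinically negative case only: 46-50 Gy in 25 fractions (5.3.3).
- Lower-neck boost limit: 4 Gy (5.3.5).
- Additional boost limit: 4 Gy, with a 70 Gy maximum (5.3.6).
- Lower-neck base dose when nodes are positive: not stated.

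**The plan's own figures.** 35 × 2 = 70 Gy, which reproduces the nodal total. 25 × 2 = 50 Gy, which reproduces the upper end of 46-50 Gy; at 2 Gy per fraction, 46 Gy is 46 / 2 = 23 fractions.

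**Test of agreement.** Let B be the base dose and b the boost, with b between 0 and 4 Gy. Section 5.3.3 requires B + b = 70, and 5.3.6 requires B + b to be no more than 70. With the full boost, b = 4:

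| Base B (Gy) | Source of B | B + 4 (Gy) | Against 70 Gy |
|---|---|---|---|
| 46 | lower end, clinically negative lower neck | 50 | 70 − 50 = 20 short |
| 50 | upper end, clinically negative lower neck | 54 | 70 − 54 = 16 short |
| 66 | stated nowhere (70 − 4) | 70 | equal |
| 70 | nodal total in 5.3.3 | 74 | 74 − 70 = 4 above |

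From a base of 46-50 Gy, the supplement needed to reach 70 Gy is 70 − 50 = 20 to 70 − 46 = 24 Gy, which is five to six times the limit.

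**Boosts smaller than 4 Gy.** The conditions hold together only for B from 66 to 70 Gy with b = 70 − B. At B = 70 this means no boost at all, so the allowances in 5.3.5 and 5.3.6 have nothing to act on, and any posterior-field dose must form part of the 70 Gy. No value of B from 66 Gy up to just below 70 Gy is stated as a lower-neck base.

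**The case against.** The strongest reply is that the low figure rests on a base the protocol does not assign to these patients. The 46-50 Gy lower-neck dose is for the clinically negative case, and the whole-neck 46-50 Gy is a minimum. Section 5.3.5 states no total, so the 16-20 Gy difference appears only once its limit is joined to a dose from 5.3.3. Nor does 5.3.5 say outright that the supplement and the boost are the same thing. Section 5.3.4.1 has every field treated at every session, and 5.3.7 gives a prescription rule for paired anterior-posterior lower-neck fields. The posterior field could therefore be part of routine delivery, with 4 Gy limiting only something further. IMRT is allowed and carries no such limit, and 5.3 leaves radiation to institutional standard practice.

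Much of this stands, and it rules out two stronger readings. A reader might infer that the protocol makes 70 Gy unreachable for positive lower-neck nodes. The documents do not support that, because the base dose is unstated. A reader might also infer that two patients could be treated 16-20 Gy apart with both plans within protocol. They could not: a plan stopping at 50-54 Gy would breach 5.3.3, which states 70 Gy for positive nodes twice.

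The reply does not bring the sections into agreement. If routine delivery already gives 70 Gy and the 4 Gy is additional, the total is 74 Gy and 5.3.6 is exceeded. Treating supplement and boost as one is also the natural reading of consecutive sentences. IMRT narrows the scope but does not close the gap, since conventional fields remain permitted and the Low Neck text sends a matched anterior field back to the same unclear doses. A general appeal to institutional practice does not settle numerical limits that the protocol sets itself.

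**Conclusion.** The inconsistency is real for conventional-field treatment. No base dose stated in the documents allows the 70 Gy nodal total, a 4 Gy boost and the 70 Gy maximum to be applied together. The size depends on the missing base: 16-20 Gy below the nodal total if the clinically negative lower-neck dose is used, 4 Gy above the maximum if 70 Gy is used, and agreement with the full boost only at an unstated 66 Gy.

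The shortfall rests on two assumptions: that 46-50 Gy is the base, and that supplement and boost in 5.3.5 are the same quantity. The overshoot assumes that the 4 Gy is given in full on top of 70 Gy and that the 5.3.6 maximum governs it. The documents do not say how many of the 31 phase II patients would have positive lower-neck nodes treated this way, so no effect on 1-year locoregional PFS can be estimated. The point should be corrected because it concerns delivered dose and a locoregional endpoint; it does not show that the trial's primary analysis is invalid.

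**What to change.** The sponsor's radiation oncologists must reconcile 5.3.3, 5.3.4.1, 5.3.5, 5.3.6 and the Low Neck text under 5.3.11. For clinically positive lower-neck nodes, the revised text should state:

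- one total dose, the base dose of the lower-neck field, and a boost limit consistent with both;
- whether the posterior-field supplement in 5.3.5 is the same thing as the boost limited there, and whether the 5.3.6 maximum includes it;
- how these apply under each permitted technique: conventional fields, IMRT, and a matched anterior field alongside IMRT.

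Which dose is right is for those specialists, and no value is proposed here. The cost is a protocol clarification, with no change to sample size or analysis.
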